## References

American College of Sports Medicine. (2021). *ACSM’s guidelines for exercise testing and prescription, eleventh edition*. Philadelphia: Wolters Kluwer.

Centers for Disease Control and Prevention. (2021, October 20). *Radiation and Your Health*. U.S. Department of Health and Human Services. Retrieved October 13, 2022 from [cdc.gov/nceh/radiation/dexa-scan.html](https://cdc.gov/nceh/radiation/dexa-scan.html)

Community Health Needs Assessment 2019. (2018). Peninsula Regional Medical Center and Wicomico and Somerset County Health Department.  
<https://somersethealth.org/wp-content/uploads/2017/03/community-health-needs-assessment-2019.pdf>

*Department of Kinesiology*

[REDACTED]

[REDACTED]

[REDACTED]

“The Implementation Of A Community Health-focused Intervention Using Combined Aerobic and Resistance Training Protocols In A Group Setting”

Date: February 21, 2023

Subject: Amendment to IRB Protocol #11-2022-004

---

This amendment requests the additional use of a Bod Pod to assist in analyzing body composition periodically, at the 8-week point and again at the 12-week point. The 8-week point would be the second week of March and the 12-week point would be the first week of April. The principal investigator (PI), myself, will operate the bod pod. The PI completed the 2-hour training session with the representative from COSMED, the Bod Pod manufacturer. The Bod Pod is in the new School of Pharmacy and Health Professions building in room 3114, on the campus of University of Maryland Eastern Shore, registered to the department of kinesiology room. The Bod Pod is a large egg-shaped device that uses air displacement to calculate body density (body mass/volume). The device predicts body fat percent and fat free mass from various body density equations depending on the subject’s race or ethnicity, age, gender, and predicted thoracic gas volume. The thoracic gas volume may be predicted and determined by the device, or it may be completed manually. This protocol will have the Bod Pod device predict and determine thoracic gas volume while the subject is sitting inside the Bod Pod.

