To increase the accuracy of the Bod Pod, subjects must wear tight-fitted clothing such as spandex/tights or single-layer compression shorts and a sports bra or camisole for females. The subject’s hair is also secured under a tight-fitted cap supplied by the department of kinesiology. The department will supply each participant their own plastic shower cap to put between their hair and the required tight-fitted cap that comes with the Bod Pod. Jewelry is not allowed to be worn and cell phones cannot be taken inside the chamber. Socks may not be worn either. The subject’s body weight is measured by a scale that is calibrated for use with the Bod Pod. The subject will be asked to stand on the scale and then step off the scale once body weight has been determined. The body weight will automatically be loaded to the software program on the connected computer. The software program is called Omnia which is where all the information collected will be stored. The computer that includes this software program is

username and password protected. Five individuals, including myself, know the username and password to log on to the computer to access the software. The individuals who know the log in information work in the department of kinesiology. The computer is attached to the Bod Pod and therefore, it cannot be removed from the room. The room is locked at all times. The administrative assistant in the office of the dean and, potentially, the campus police are the only individuals who have access to the room. Neither know the username nor password for the computer.

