After stepping off the scale, the subject would then be asked to step in and sit in the Bod Pod chamber which includes a large glass window for the participant to look out of. The subject will be instructed to sit and remain still as possible while the analysis is taking place. The Bod Pod door will be closed and opened following on-screen prompts. The door will be opened twice in timed intervals while the subject remains seated and still as possible. The door opening and closing allows the Bod Pod device to calculate consistent readings in terms of the air that has been displaced by the subject sitting inside the chamber. The subject will be told that the entire process takes about three minutes, if there are no interruptions or errors with the device causing a repeat of the steps, including all the intervals with the door opening and closing. Once the on-screen prompt says the analysis is complete, the PI will open the door and allow the subject to put any additional clothing back on. The results will then be shared with the subject. The results may also be printed out for the subject and the PI to receive a copy. Individual subject data from the analysis will be identified on the software program as colors. The PI will have a key for these colors. The key will identify which color goes with which subject's middle name. The subject's middle name was initially used during the first week of the pre-assessment and preliminary fitness test. A color is now being used as a second layer since four other departmental members have access to the Bod Pod device and software program. The PI will not share the colors with anyone. The key for the colors and the Bod Pod analysis will be kept in the locked cabinet where the signed informed consents are.

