Since jewelry cannot be worn, the subject will be asked to place their jewelry in a safe place with the other belongings that he/she has brought to the analysis session. Since the subject may be uncomfortable with this, the PI will re-emphasize that the analysis is about three total minutes, if there are no interruptions or errors with the device causing a repeat of the steps, and they are free to put the jewelry back on as soon as the chamber door opens back up at the conclusion of the analysis. Since a cellphone cannot be taken inside the chamber, the participant will be asked to place their cellphone in a safe place and/or in a place that is comfortable for him/her. When the chamber door opens at the end of the analysis, the PI will allow the subject an opportunity to get their jewelry and cellphone prior to any discussions about the analysis if that is what the subject desires to do. Socks may also not be worn during the analysis and therefore the PI will clean the floor on the inside of the chamber with a Clorox wipe while in the presence of the subject. On the contrary, the subject will be allowed to wear their socks while they are on the body weight scale. The restriction of jewelry, cellphones, and socks may also present risks for the subject that include a lack of comfort related to losing or forgetting something that is valuable. The PI will allow the subject to take off or put away all items right before entering the chamber and the PI will allow the subject to return and get all items right after the analysis is complete and the chamber door opens. The PI will wipe the floor in the chamber with a Clorox wipe and dry it with a paper towel so that the participant can see the floor has been sanitized.

Benefits associated with the addition of this body composition device have to do with its level of accuracy comparable to bioelectrical impedance analysis devices. Measuring body density is used as a criterion standard for assessing body composition. Underwater weighing and DEXA have since been considered the criterion measure. However, use of the Bod Pod reduces the challenges/risks associated with being submerged in water and/or being exposed to radiation (ACSM, 2021). The inclusion of the Bod Pod allows the body composition results to be more reliable.

American College of Sports Medicine. (2022). *ACSM's guidelines for exercise testing and prescription 11th edition*. Philadelphia: Wolters Kluwer.

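### The Bod Pod amendment allows socks on the scale but not in the chamber, and does not clearly say that jewelry and phone are off at weighing, so percent fat can be slightly understated

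*Combined protocol and SAP*

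**What the plan says.** All of this is in the Bod Pod amendment (Amendment to IRB Protocol #11-2022-004), which adds tests at weeks 8 and 12.

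- **Quantity measured.** The device "uses air displacement to calculate body density (body mass/volume"). "The device predicts body fat percent and fat free mass from various body density equations"; the equation to be used is not named.
- **Mass.** The subject's "body weight is measured by a scale that is calibrated for use with the Bod Pod". "The body weight will automatically be loaded to the software program on the connected computer". No tare or correction for worn items is described.
- **Order.** "After stepping off the scale, the subject would then be asked to step in and sit in the Bod Pod chamber".
- **Socks.** They are barred during the analysis, yet "the subject will be allowed to wear their socks while they are on the body weight scale".
- **Jewelry and phone.** The attire paragraph says "Jewelry is not allowed to be worn and cell phones cannot be taken inside the chamber". The later paragraph on personal belongings names jewelry, phones and socks together and then says: "The PI will allow the subject to take off or put away all items right before entering the chamber".

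No sentence requires jewelry or phone to be off at the scale. None requires a subject to wear the same items at both tests.

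**The concern.** Density is a ratio, so its numerator and denominator must describe the same person in the same state. Here the mass may include socks while the volume never does. Extra mass over an unchanged volume raises the computed density. Under any equation in which percent fat falls as density rises, it therefore lowers percent fat and raises fat-free mass. The error has a known direction, so it does not average out across subjects.

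The amendment justifies the Bod Pod by more reliable body-composition results, and it controls food, exercise and clothing to that end. Results are shown to the subject. A sock rule that works against the measurement is at odds with that purpose and is easily removed.

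**Working it through.** The documents give no item weight, error size, expected change or standard deviation, so there is no stated figure to reproduce. The size has to be worked out under assumptions.

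**Inputs from the amendment:** density is mass over volume; mass comes from the scale, before the chamber; volume is taken without socks; readings are at weeks 8 and 12.

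**Assumptions:** the two-compartment conversion %fat = 495/D − 450 (fat density 0.9, lean density 1.1); body mass M of 60 to 120 kg; true fat P of 25 to 45%; socks of m = 30 to 100 g.

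**Error at one test.** True density is D = 495/(P + 450) and volume is V = M/D. The device sees D_obs = (M + m)/V. Substituting gives

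error in %fat = −(P + 450) × m/(M + m).

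Example at 80 kg, 35% fat and 50 g: D = 495/485 = 1.0206, and D_obs = 1.0206 × 80.05/80 = 1.0213. The error is −485 × 0.05/80.05 = −0.30 points, so 35.0% is reported as 34.7%.

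| Body | 30 g | 50 g | 100 g |
|---|---|---|---|
| 60 kg, 25% | −0.24 | −0.40 | −0.79 |
| 60 kg, 45% | −0.25 | −0.41 | −0.82 |
| 80 kg, 35% | −0.18 | −0.30 | −0.61 |
| 120 kg, 25% | −0.12 | −0.20 | −0.40 |
| 120 kg, 45% | −0.12 | −0.21 | −0.41 |

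The range for socks is therefore 0.12 to 0.82 points.

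**In kilograms.** Computed fat mass is (4.95/D_obs − 4.5) × (M + m) = 4.95V − 4.5(M + m). Each 100 g of unmatched mass removes 0.45 kg of computed fat and adds 0.10 + 0.45 = 0.55 kg of computed fat-free mass, at any body size.

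**Week 8 to week 12 change.** Take 80 kg at both tests and a true change from 35 to 34% (−1.0 point):

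- 50 g at both tests: 34.70 to 33.70, change −1.0. The error nearly cancels.
- 50 g at week 8 only: 34.70 to 34.00, change −0.7.
- 50 g at week 12 only: 35.00 to 33.70, change −1.3.

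**Hypothetical upper case.** If socks, jewelry and a phone weighing 300 g together were all on the scale, the error at 80 kg and 35% fat would be −485 × 0.3/80.3 = −1.81 points. Over the same range of bodies it would be 1.18 to 2.46 points. With 300 g at one test only, the true change of −1.0 would read as +0.81 (week 8 only) or −2.81 (week 12 only).

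**After the fix,** m = 0 and this error is zero.

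**The case against.** The strongest reply is that only socks are expressly allowed on the scale. The attire paragraph bars jewelry without limiting the bar to the chamber, and it does so before the weighing step is described. The sock permission is worded as an exception, which would be unnecessary if everything could stay on at weighing. Subjects are in tight-fitting clothing and are asked to put the phone somewhere safe, so a phone on the scale is unlikely. The sentence on removal before the chamber addresses worry about losing valuables; it is permissive and was not written to set the order of weighing.

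All of this stands. A reader might infer that subjects are weighed with jewelry and phone on. The text does not say so; it only fails to exclude it clearly. Nor is it shown that every reading is biased, since socks on the scale are optional. That the bias differs between visits is not stated either; it is merely not prevented. Any suggestion that the error could match a real four-week change would rest on an assumed phone and on an expected change that the documents do not give.

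The consequence for the study is also limited. The Bod Pod has no pre-intervention reading, the before-and-after body-composition measure is BIA (sections 3 and 9), and the amendment adds no analysis of Bod Pod values. Subjects are to be told to treat their results as motivation only.

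The reply does not remove the sock rule. It is written, it applies to mass and not to volume, and no correction is described.

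**Conclusion.** The point holds for socks as written, and for jewelry and phone only as an ambiguity. Following the amendment can overstate density and understate percent fat by about 0.1 to 0.8 points through socks alone. That size rests on assumed sock weights of 30 to 100 g, an assumed two-compartment equation, and bodies of 60 to 120 kg at 25 to 45% fat. The direction needs only that percent fat falls as density rises. Errors above 1 point need heavier items on the scale and remain hypothetical.

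Individual values shown to subjects can be biased. The week 8 to week 12 change is nearly free of this error if the same items are worn at both tests, but no rule secures that. Severity is minor: the documents do not show that any planned pre-post comparison is affected.

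**What to change.** In the amendment:

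1. Delete the permission "the subject will be allowed to wear their socks while they are on the body weight scale".
2. In the sentence "The PI will allow the subject to take off or put away all items right before entering the chamber", move the time of removal to immediately before the subject steps on the scale. Make the attire paragraph agree, so that the jewelry, phone and sock rules plainly cover weighing.
3. State that the subject goes from scale to chamber wearing exactly the same items, at both visits.
4. Wipe the scale platform, as is already planned for the chamber floor.

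The change should be in force before the week 8 tests, because introducing it between the two tests would itself create the one-visit mismatch shown above.

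The cost is a few sentences, items off slightly longer, and one more surface to wipe.
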